5.4 SCREEN FAILURES

Screen failures are defined as participants who consent to participate in the clinical trial but are not subsequently randomized to a study arm. A minimal set of screen failure information is required to ensure transparent reporting of screen failure participants to meet the Consolidated Standards of Reporting Trials (CONSORT) publishing requirements and to respond to queries from regulatory authorities. Minimal information includes demography, screen failure details, eligibility criteria, and any serious adverse event (SAE).

Individuals who do not meet the criteria for participation in this trial (screen failure) due to failing to meet entry criteria, may be rescreened and considered for study participation. Rescreened participants should be assigned the same participant number as for the initial screening.

5.5 STRATEGIES FOR RECRUITMENT AND RETENTION

Multiple recruitment strategies are planned using the IRB approved recruitment material. Our primary recruitment approach will be to contact participants already known to the Sjögren's syndrome NIDCR clinical protocols (15-D-0051 and 11-D-0172) where participants have consented to be contacted regarding future studies.

Additional methods for recruitment will include contacting patient support groups (e.g., Sjogren's Foundation) as well as contacting referring physician groups to advertise and potentially refer participants. We will utilize the services of NIH Clinical Center Office of Patient Recruitment and adhere to the NIH Clinical Center Media Policy. Various NIDCR social media platforms which adhere to NIH and the IC's social media guidelines may also be used.

Abbreviated Title: Tofacitinib in Sjögren's syndrome

Version Date: 07/01/2024

For recruitment, the study team will ensure that social and new media applications and accounts are set up and managed in accordance with Section 508 of the Rehabilitation Act of 1973: guidance available at <http://www.hhs.gov/web/508/index.html> and HHS policy available at <https://intranet.hhs.gov/it/strategy-policy-governance/policies-standards-guides/508-accessibility-of-technology.html>. For all the recruitment strategies, we will use the approved recruitment materials.

Target Patient Samples Size by Gender and Race and Ethnicity: 30 total patients which will include approximately 27 females and 3 male participants, which reflects the typical female: male distribution of patients in our clinic. We anticipate that 10% of our participants will be non-white reflecting our current racial-ethnic distribution in our clinic.

Participants may also be recruited:

- Outpatient Sjögren's syndrome and Salivary Disorders Clinic, or Rheumatology Clinic of the Clinical Center at the NIH or the NIAMS Community Health Center;
- Participants referred for treatment and/or second opinion to the NIH;
- Local area rheumatologists, internists, dental practices, and university hospital clinics;
- Participants that are referred by their local providers, we will requested to contact the research coordinator directly to initiate a release of medical records for review for study eligibility. Consistent with our current research protocols in this study population, we expect the sending provider has obtained a signed HIPAA authorization or other type of signed medical release of information (if under the Privacy Act or outside of the US) to be able to share these records or specimens with the study coordinator.

5.5.1 Recruitment of women, children, and minorities:

Minors and pregnant women will not be included in this study. This is a Phase Ib-IIa study involving greater than a minor increment over minimal risk without the prospect of direct benefit to participants based on currently available data. The sex distribution (female: male) for SS is 9:1; recruitment is expected to support this distribution.

5.5.2 Costs

We do not anticipate any direct costs for study participation.

5.5.3 Compensation

Participants will receive financial compensation for time required to participate in the research as per NIH guidelines. The participants will be paid \$130 at each outpatient visit. In addition, participants will be paid an additional \$100 at the end of study visit Day 196 as a study completion bonus. Patients who receive a second (or additional non-diagnostic biopsy) biopsy will be paid \$220 for each additional salivary gland biopsy. Any participant who withdraws from study will be paid for the number of visits completed. For participants living outside a 45-mile radius, travel compensation may be provided at discretion of the principal investigator.

Meal cost will be reimbursed up to \$50.00 USD a day per participant per study visit for participants travelling from outside a 45-mile radius to the Clinical Center.

6 STUDY INTERVENTION

6.1 STUDY INTERVENTIONS(S) ADMINISTRATION

Tofacitinib (Pfizer, Inc.) is a Janus kinase (JAK) inhibitor. JAKs are intracellular enzymes that transmit signals arising from cytokine or growth factor-receptor interactions on immune cell membranes to influence cellular processes of haematopoiesis and immune cell function. Within the signalling pathway, JAKs phosphorylate and activate Signal Transducers and Activators of Transcription (STATs) which modulate intracellular activity including gene expression.

Tofacitinib modulates the signalling pathway at the point of JAKs, preventing the phosphorylation and activation of STATs.

Tofacitinib citrate is a white to off-white powder with the following chemical name: (3R,4R)-4-methyl-3-(methyl-7H-pyrrolo [2,3-d]pyrimidin-4-ylamino)-β-oxo-1- piperidinepropanenitrile, 2-hydroxy-1,2,3-propanetricarboxylate (1:1) It is freely soluble in water and has a molecular weight of 504.5 Daltons. Tofacitinib is supplied for oral administration as 5 mg white round, immediate-release film-coated tablets. Each tablet of Tofacitinib contains the appropriate amount of Tofacitinib citrate salt and the following inactive ingredients: microcrystalline cellulose, lactose monohydrate, croscarmellose sodium, magnesium stearate, HPMC 2910/Hypromellose 6cP, titanium dioxide, macrogol/PEG3350, and triacetin.

There will be no IND obtained for the use of any of the investigational agents used in this study.

This study meets the criteria for exemption for an IND as this investigation is not intended to support a new indication for use or any other significant change to the labeling; the drugs are already approved and marketed and the investigation is not intended to support a significant change in advertising; and the investigation does not involve a route of administration or dosage level in use in a patient population or other factor that significantly increases the risks (or decreases the acceptability of the risks) associated with the use of the drug product. The Food and Drug Administration was contacted on 12/18/2019 for a determination for IND and approved a waiver on 01/23/2020; a copy of the FDA IND waiver for IND is provided.

6.1.1 Dosing and Administration

The package insert with the recommended dosing is provided. Each participant will be dosed with 5 mg (1 tablet) twice daily for 168 days as is recommended for the treatment of rheumatoid arthritis. Tofacitinib and placebo tablets will be supplied by Pfizer Incorporated to the NIH Clinical Center Research Pharmacy.

6.1.2 Participant Dosing Considerations

Participants entering the study will have mild to moderate disease activity. Based on the known response to Tofacitinib in RA, animal studies, and cellular assays; we expect a similar rapid response in SS participants.

- Any participants experiencing a flare of glandular or extra-glandular manifestations of Sjögren's syndrome, evaluated by the PI or the medically-responsible investigator will be re-evaluated in two (2) weeks (14 days). Study drug will be continued during the monitoring period. If disease activity continues to worsen, the participant will be withdrawn from the study as per Section 7.

Abbreviated Title: Tofacitinib in Sjögren's syndrome

Version Date: 07/01/2024

- Participants with absolute neutrophil count (ANC) 500 to 1000 cells/mm³, will have study drug dosing interrupted until absolute neutrophil count (ANC) is greater than 1000 within 28 days; at that time study drug dosing will resume at 5 mg, orally, twice daily. Otherwise, participants will be withdrawn per Section 7.
- Participants with hemoglobin less than 8 g/dL or a decrease of more than 2 g/dL from baseline will have study drug dosing interrupted and held until hemoglobin values have at least returned to baseline within 28 days at which time study drug will be reintroduced. Otherwise, participants will be withdrawn per Section 7.
- Study drug may be interrupted at the discretion of the investigator if it is in the best interest of the participant.

Drug Administration

A 35-day supply of study drug or placebo will be dispensed to participants on study days 1, 28, 56, 84, 112,140 visits as well as unscheduled visits, if required with instructions regarding the twice daily dosing regimen and a review of potential side effects. No drug will be dispensed to a female participant of reproductive potential until negative pregnancy test results (serum or urine) have been obtained within 24 hours of on site visit.

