7 STUDY INTERVENTION DISCONTINUATION AND PARTICIPANT DISCONTINUATION/WITHDRAWAL

7.1 DISCONTINUATION OF STUDY INTERVENTION

Discontinuation from study intervention does not mean discontinuation from the study, and remaining study procedures should be completed as indicated by the study protocol. Once enrolled, should study participant evidence a clinically significant finding, the PI or Medically Responsible Investigator will determine if any change in participant management is needed.

An investigator may discontinue study intervention in a participant for the following reasons:

- Completion of study intervention
- Disease progression which requires discontinuation of the study intervention
- If any clinical adverse event (AE), laboratory abnormality, or other medical condition or situation occurs such that continued participation in the study would not be in the best interest of the participant
- Investigator discretion as in Sections 6.4, 6.5 and 7.2
- Positive pregnancy test
- Lymphocyte count less than 500 cells/mm³, confirmed by repeat testing
- ANC less than 500 cells/mm³, confirmed by repeat testing

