7.2 PARTICIPANT DISCONTINUATION/WITHDRAWAL FROM THE STUDY

Prior to removal from study, effort must be made to have all subjects complete a safety visit approximately 14 days (+14 days) following the last dose of study therapy. Participants are free to withdraw consent at any time upon request. Participants may also choose to withdraw treatment but remain in the study for follow up. Participants must be withdrawn consistent with Section 6.1.2. Additionally, the PI or Medically Responsible Investigator may also choose to withdraw treatment or withdraw a participant from the study based on clinical or professional judgement. An investigator may withdraw treatment or a participant from study for the following reasons:

- Request by participant to be withdrawn from the study.
- Flares not resolving within 28 days or if, in the opinion of the medically-responsible investigator, the participant requires immediate immunosuppressive therapy that is not allowed in the protocol.
- Any Grade 4 adverse event that is unexpected and at least possibly related to study drug.
- More than 45 days delay in treatment after the screening visit.
- More than one (1) "no-show" for a visit.
- Persistent elevation of LFTs of > 2 times upper limit of normal persistently present on repeated samples 14 days +/- 7 days apart.

- >30% increase in serum creatinine from baseline at enrollment, persistently present on repeated samples 14 days +/- 7 days apart.
- Increase in proteinuria at the time of screening visit to protein to creatinine ratio of more than 1.000 mg/dL or more than 1000 mg in a 24 hours urine collection, persistently present on repeated samples 14 days +/- 7 days apart.
- Any other reason that, in the opinion of the responsible Investigator or Medically Responsible Physician, poses unacceptable risk to the participant.
- Infections requiring intravenous antibiotic treatment.
- Development of any malignancy.
- Urine BK virus level of more than 10 million copies/ml by quantitative PCR or detection of BK virus in serum by quantitative PCR.
- Non-compliance with treatment (<80% compliance by pill count).

The reason for participant discontinuation or withdrawal from the study will be recorded on the Voluntary Study Withdrawal Case Report Form (CRF). Participant who signs informed consent and are randomized, but do not receive the study drug, may be replaced.

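### The mandatory ANC hold has a floor at 500, so a first count below 500 carries no required interruption, only a permissive stop after an untimed repeat

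*Combined protocol and SAP*

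**What the plan says.** Section 6.1.2 sets the ANC hold: "Participants with absolute neutrophil count (ANC) 500 to 1000 cells/mm³, will have study drug dosing interrupted". Dosing resumes if the count rises above 1000 within 28 days; otherwise the participant is withdrawn. The next bullet covers haemoglobin: "Participants with hemoglobin less than 8 g/dL or a decrease of more than 2 g/dL from baseline will have study drug dosing interrupted". The list ends with a general permission: "Study drug may be interrupted at the discretion of the investigator if it is in the best interest of the participant".

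Counts below 500 appear in Section 7.1. The lead-in is "An investigator may discontinue study intervention in a participant for the following reasons", and the list includes "ANC less than 500 cells/mm³, confirmed by repeat testing" and "Lymphocyte count less than 500 cells/mm³, confirmed by repeat testing". Neither item says when the repeat is due or what happens to dosing meanwhile. The same section says that, for a clinically significant finding, the PI or Medically Responsible Investigator "will determine if any change in participant management is needed".

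Section 7.2 has no ANC or lymphocyte criterion. For liver tests, creatinine and proteinuria it does time the repeat: the abnormality must be "persistently present on repeated samples 14 days +/- 7 days apart".

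**The concern.** A hold rule should not weaken as the value gets worse. Here the milder range carries an immediate instruction that rests on one value. The more severe range carries none until a second value arrives at an unspecified time, and even then the wording is permissive. Dosing between the two values is left to judgement.

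Safety is the primary objective, and the hold and stop rules are what protect participants while those data accrue. Lymphocytes below 500 share two of the defects (the untimed repeat and the permissive wording), although there is no lymphocyte hold band to fall out of. The lymphocyte item has the clearer clinical link: Section 2.4.1 ties counts below 500 to serious infection, and reports no clear association between neutropenia and infection.

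**Working it through.** The protocol gives no figure to reproduce. The check is a comparison of its rules, followed by a small calculation for scale.

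**1. Required action by ANC (cells/mm³)**

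| ANC | Action required | Source |
|---|---|---|
| Above 1000 | None | – |
| 500 to 1000, single value | Hold; withdraw if not above 1000 within 28 days | 6.1.2 |
| Below 500, first value | None | – |
| Below 500, confirmed at an unstated time | Discontinuation permitted | 7.1 |

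**2. Neighbouring rules.** The haemoglobin hold has no floor and acts on one value. The 7.2 criteria for liver tests, creatinine and proteinuria state a repeat interval. So the authors used both open-ended holds and timed repeats elsewhere, and nothing explains their absence here.

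**3. Does another provision oblige a hold?**
- The last item of 6.1.2 permits an interruption.
- 7.1 asks for a management decision, and also lists laboratory abnormalities that make continuing not in the participant's interest, under the same permissive lead-in.
- 8.6.4 requires results to be evaluated for clinical significance.
- 6.2.1 makes dispensing depend on investigator approval. That is a real check at dispensing visits, but Day 14 has a blood count and no dispensing (1.3, 8.2.1).
- 7.2 makes withdrawal mandatory where 6.1.2 calls for it, and 6.1.2 is silent below 500.

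Each of the first four allows or prompts a hold. None requires one.

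**4. How often it could arise.** Inputs: 20 tofacitinib participants (4.1). From the cited rheumatoid arthritis data in 2.4.1, over the first three months: ANC below 1000 in 0.07%, no ANC below 500, lymphocytes below 500 in 0.04%. The ANC rate is a ceiling for counts below 500.
- ANC: 20 × 0.0007 = 0.014 expected; P(at least one) = 1 − 0.9993^20 = 1.4%.
- Lymphocytes: 20 × 0.0004 = 0.008 expected; 1 − 0.9996^20 = 0.8%.

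Scaled to 168 days at a constant rate (an assumption, with three months taken as 91 days), the factor is 168/91 = 1.846:
- ANC: 0.0007 × 1.846 = 0.00129; 1 − (1 − 0.00129)^20 = 2.6%.
- Lymphocytes: 0.0004 × 1.846 = 0.00074; 1 − (1 − 0.00074)^20 = 1.5%.

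**The case against.** The best defence is that this is an ordinary two-tier rule: hold at 500 to 1000, stop below 500. The permissive lead-in in 7.1 is generic, since it also introduces completion of treatment and a positive pregnancy test. An investigator who saw a count of 400 would very probably hold drug at once. Many falling counts would also pass through the hold band first. Sections 4.3 and 6.1.1 refer to a package insert that is not reproduced and may cover this step. All of this stands, and it limits the point to what the text *requires* between a first value and its repeat.

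The Grade 4 criterion in 7.2 might also apply. Under 8.7.3 an event is unexpected if its severity exceeds the described risk, and no ANC below 500 had been reported. This assumes such a count is Grade 4, since the grading table is not reproduced. The criterion is itself permissive, so it does not close the gap.

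Three stronger readings are tempting, and the documents do not support them.
- **That the plan intends dosing to continue below 500.** The 7.1 item points to discontinuation as the intent.
- **That a participant could be dosed for one to three weeks while a repeat is awaited.** That borrows the 7.2 interval, which the plan does not apply to ANC, and it needs an investigator to decline every available hold.
- **That a directed hold would trigger withdrawal under the 80% compliance rule.** Section 6.4 has the PI judge compliance on several factors besides the pill count, and 6.6 itself allows a one-week pause for a COVID-19 booster.

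**Conclusion.** The gap in the wording is real: no provision in the protocol obliges a hold on a first ANC below 500, and the repeat that would lead to a stop has no deadline. It is a minor correction to a safety rule. It touches no endpoint or analysis.

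The frequency figures assume that rheumatoid arthritis rates carry over to Sjögren's syndrome. Section 2.4.1 says there are no data on tofacitinib in this disease, and exclusion criterion 10 admits participants with an ANC as low as 1000, so the true rate could differ.

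Time also limits the benefit. The version date (07/01/2024) is 81 days before the stated end date (09/20/2024). Allowing for the 28-day follow-up, the last dose would fall about 81 − 28 = 53 days after the version date, less the time for IRB approval, unless the study is extended. The wording is still worth correcting for anyone on drug, and before it is reused in the larger study that 4.2 foresees.

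**What to change.** **Section 6.1.2.** Change the trigger to any ANC of 1000 or below, with drug held from the first value. This only removes the floor; the upper limit and the 28-day rule stay.

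**Section 7.1.** For ANC or lymphocytes below 500, require a repeat within a stated few days. The 14 ± 7 days of 7.2 is too long for counts this low. The interval should run to review of the result, because 10.5 allows local laboratories 7 business days (± 7 days) to report. State that drug will be discontinued if the value is confirmed.

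**ANC outcomes after the repeat.** Above 1000, resume. From 500 to 1000, stay on hold under the existing 28-day rule. Below 500, discontinue.

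**Lymphocytes.** The prompt repeat and the firm stop on confirmation are enough. An automatic hold on one unconfirmed value is not needed: 2.3.1 notes that lymphopenia is associated with the disease itself, and participants may enter with a count of 500. Discretion to hold remains.

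**Cost.** A wording amendment with IRB review, an occasional extra blood count (already possible at unscheduled visits or local laboratories), and rare missed doses when a first ANC below 500 proves transient.

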6.2 PREPARATION/HANDLING/STORAGE/ACCOUNTABILITY

Tofacitinib five (5) milligram (mg) tablets are white, round, immediate release film-coated tablets, debossed with “Pfizer” on one side and “JKI 5 on the other side. Tofacitinib tablets will be stored at 20°C to 5°C (68°F to 77°F) as per manufacturer’s recommendations included in labelling.

6.2.1 Acquisition and Accountability

Pfizer is providing seventy-count (#70) labelled bottles of 5 mg Tofacitinib and placebo. These bottles will be dispensed monthly to the study participants by pharmacy after protocol mandated visit is completed and all clinical and study parameters meet approval of the PI or AI seeing the participant.

6.2.2 Formulation, Appearance, Packaging, and Labeling

Tofacitinib tablets contain 5 mg Tofacitinib. They are white, round, immediate-release film coated tablets, debossed with “Pfizer” on one side, and “JKI 5” on the other side.

6.2.3 Product Storage and Stability

The drug and placebo will be stored in the NIH Pharmacy according to the manufacturer’s suggested storage conditions.

6.2.4 Preparation

Study drugs are provided in the expected quantity and preparation.

6.3 MEASURES TO MINIMIZE BIAS: RANDOMIZATION AND BLINDING

Randomization will be done by the NIH Clinical Research Center Pharmacy in conjunction with the statistician associated with the study. This is a two-arm, double blind study.

The study will utilize the stratified block randomization method to ensure that the Tofacitinib and placebo groups are balanced with respect to the baseline disease activity level. Eligible

Abbreviated Title: Tofacitinib in Sjögren's syndrome

Version Date: 07/01/2024

subjects will be stratified according to the ESSDAI score (0-1 vs. 2-13). Within each stratum, subjects will be randomly assigned by use of computer-generated blocks of size 3 with a 2:1 ratio to Tofacitinib or control group. Thus, participants will be randomized to either Tofacitinib or placebo in a 2:1 ratio overall. Both participants and investigators will be blinded to treatment allocation. Unblinding for analysis will occur once all the collected study data has been entered and the database is locked. Participants and local treating physicians will be informed of treatment allocation by a letter sent by certified mail, at that time.

The blind will be held by the statistician and the NIH Clinical Center Research Pharmacy. In cases where breaking the blind is necessary to provide clinical care to the participant, as determined by the PI and medically responsible team member, [name], the PI will contact the NIH Clinical Center Research Pharmacy and provide the treatment allocation information to the treating physician. Such participant(s) would be withdrawn from the study and followed up as described in section 4.10 above.

The Data and Safety Monitoring Committee (DSMC) may also request unblinding of treatment allocation or group assignment. These requests will be transmitted to the NIH Clinical Center Research Pharmacy by the PI. Data will be provided directly to the DSMC Chair without unblinding the investigators before the DSMC determines a plan of action.

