8.7.2 Relationship to Study Intervention

All adverse events (AEs) must have their relationship to study intervention assessed by the investigator who examines and evaluates the participant based on temporal relationship and his/her clinical judgment. The degree of certainty about causality will be graded using the categories below. In a clinical trial, the study product must always be suspect.

For all AEs and SAEs, the investigator will provide his best estimate of the causal relationship between the event and study drug, and the causal relationship between the event and study procedures. The degree of certainty about causality will be graded according to the following criteria.

- **Definitely Related** – There is clear evidence to suggest a causal relationship, and other possible contributing factors can be ruled out. The clinical event, including an abnormal laboratory test result, occurs in a plausible time relationship to study intervention administration and cannot be explained by concurrent disease or other drugs or chemicals. The response to withdrawal of the study intervention (dechallenge) should be clinically plausible. The event must be pharmacologically or phenomenologically definitive, with use of a satisfactory rechallenge procedure if necessary.
- **Probably Related** – There is evidence to suggest a causal relationship, and the influence of other factors is unlikely. The clinical event, including an abnormal laboratory test result, occurs within a reasonable time after administration of the study intervention, is unlikely to be attributed to concurrent disease or other drugs or chemicals, and follows a clinically reasonable response on withdrawal (dechallenge). Rechallenge information is not required to fulfill this definition.
- **Possibly Related** – There is some evidence to suggest a causal relationship (e.g., the event occurred within a reasonable time after administration of the trial medication). However, other factors may have contributed to the event (e.g., the participant's clinical condition, other concomitant events). Although an AE may rate only as "possibly related"

soon after discovery, it can be flagged as requiring more information and later be upgraded to “probably related” or “definitely related”, as appropriate.

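### Emergency code breaks give the PI the allocation, and with disclosed fixed blocks of 3 a placebo break can identify two other participants

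*Combined protocol and SAP*

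**What the plan says.** Section 6.3 sets the aim: "Both participants and investigators will be blinded to treatment allocation". It then describes two routes by which the blind can be opened before database lock.

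- **Clinical need.** The decision is shared: "In cases where breaking the blind is necessary to provide clinical care to the participant, as determined by the PI and medically responsible team member". After that, "the PI will contact the NIH Clinical Center Research Pharmacy and provide the treatment allocation information to the treating physician". The unblinded participant is withdrawn from the study.
- **DSMC request.** The PI transmits the request to the pharmacy, but "Data will be provided directly to the DSMC Chair without unblinding the investigators". This protection lasts until the DSMC has decided on a plan of action.

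The same section gives the allocation scheme in the protocol that the investigators hold: within each of two strata (ESSDAI 0-1 and 2-13), "subjects will be randomly assigned by use of computer-generated blocks of size 3 with a 2:1 ratio to Tofacitinib or control group". Under Section 8.1.1 the PI or a designated associate investigator asks the pharmacy to randomize each eligible participant.

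The judgements at issue are assigned as follows:

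- **Flares:** the PI or the medically responsible investigator (Section 6.1.2). Flares are among the primary endpoints (Section 9.1).
- **Laboratory abnormalities as adverse events:** the PI together with the medically responsible investigator (Section 8.6.4).
- **Relatedness:** the investigator who examines the participant, "based on temporal relationship and his/her clinical judgment" (Section 8.7.2). Section 6.2.1 shows that the PI is one of those who may see participants.

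**The concern.** The PI does not need the allocation to authorize a code break; only the treating physician needs the result. The protocol applies this separation to DSMC requests but not to clinical breaks.

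Withdrawing the unblinded participant does not contain the information. Block-mates may still be under assessment, and the small fixed block lets one known arm inform the others. The unblinded participant also still contributes data: Section 8.2.2 asks withdrawn participants to attend days 168 and 196, and the safety population in Section 9.2.1 keeps those who complete a safety follow-up, withdrawn or not. Nothing requires relatedness to be recorded before the code is released.

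The outcomes exposed are those that rest on judgement. These are flares, whether a laboratory change counts as an adverse event, and relatedness where the PI is the examiner. Relatedness defines toxicity in Section 3 and enters the DSMC alert criteria in Section 10.7, which the PI monitors. With 10 planned placebo participants, a few altered calls could change the look of a comparison by arm.

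**Working it through.** **Inputs.** Blocks of 3 at 2:1, two strata (Section 6.3). Planned arms of 20 and 10 (Section 4.1). Randomization requested by the PI or an associate investigator (Section 8.1.1). No expected number of code breaks is given.

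**1. The plan's own figure.** 30/3 = 10 blocks; 10 x 2 = 20 on tofacitinib and 10 x 1 = 10 on placebo. This matches Section 4.1.

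**2. What one revealed arm says about the block.** The possible sequences are PTT, TPT and TTP, each with probability 1/3.

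- Placebo revealed, in any position: one sequence remains. Both block-mates are on tofacitinib with probability 1.
- Tofacitinib revealed, in any position: two sequences remain. Each block-mate is on placebo with probability 1/2, against 1/3 before the break.

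One placebo break in a filled block thus identifies 2 of the 20 planned tofacitinib participants (2/20 = 10%), besides the participant whose code was broken.

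**3. Average per break.** If a break is equally likely for every participant, it shows placebo with probability 1/3, and the expected number of others identified with certainty is (1/3) x 2 = 0.67. The actual result is always 2 or 0. If a participant on tofacitinib is r times as likely to need a break as one on placebo, then P(placebo) = 1/(1 + 2r) and the expected number is 2/(1 + 2r). The documents give no r, so the following is a range of assumptions:

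| r | Expected others identified |
|---|---|
| 0.5 | 2/2 = 1.00 |
| 1 | 2/3 = 0.67 |
| 2 | 2/5 = 0.40 |
| 3 | 2/7 = 0.29 |

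**4. Unfilled block.** If the revealed placebo participant is first or second in a block that is still open, every remaining assignment in it is tofacitinib. The break then predicts the next allocation in that stratum, which is a loss of concealment.

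**5. What the inference requires.** The person must know the block size (stated in the protocol), the stratum (a clinical score) and the order of randomization within the stratum. Someone who requests the randomizations can plausibly know the order. Numbers must also be used in sequence, which the documents do not state, and they do not say how replacements take numbers.

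**The case against.** The best case against rests on four facts.

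- **Breaks may be rare or absent.** They require a clinical determination, and study drug can be interrupted or stopped without unblinding (Sections 6.1.2, 7.1 and 7.2). There is therefore no trial-level magnitude. This stands.
- **The PI is not the named rater of everything.** A reader might infer that the PI judges all causality and scores ESSDAI and PGA. The documents do not support that: Section 8.7.2 names the examining investigator, and no section names the ESSDAI or PGA rater. The exposure that can be shown is flares, laboratory adverse events, and relatedness where the PI is the examiner.
- **Most of the primary safety summary does not use relatedness.** A reader might infer that the primary endpoint turns on it. Sections 9.1 and 9.3.2 also report any adverse event, serious events, Grade 3 and 4 toxicities and flares by arm, and severity follows CTCAE. Relatedness drives the toxicity definition and the related-event row only. This narrows the point but leaves flares, which are also a judgement.
- **The DSMC comparison is imperfect.** That request also passes through the PI, and its protection is time-limited. It still shows that the pharmacy can release data without passing them through the investigators.

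Block-mates may also have finished, or not yet have enrolled, when a break occurs. That limits the practical effect, but it does not explain why the PI should receive the allocation.

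**Conclusion.** The point holds as a gap in procedure that is cheap to close. As written, Section 6.3 unblinds the PI at every clinical code break. Given a filled block assigned in sequence and a known randomization order, a placebo break identifies both block-mates with certainty, and a tofacitinib break moves each from 1/3 to 1/2 placebo. The average of 0.67 holds only if breaks are unrelated to arm, and it should not be read as an expected effect on the trial, because the number of breaks is unknown and may be zero.

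Section 9.1 calls all analyses descriptive, and Section 9.3.1 reserves testing for efficacy variables. The harm is therefore to the credibility of the flare and relatedness comparisons, not to a formal error rate on safety.

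**What to change.** Amend Section 6.3 so that:

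1. once a break has been authorized, the pharmacy releases the allocation directly to the treating physician;
2. the PI and any investigator who assesses outcomes are told only that a break occurred;
3. relatedness of the triggering event is recorded before release, where this does not delay care. The dated entry should be kept, because Section 8.7.2 allows a possibly related event to be upgraded later.

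The PI can still take part in deciding on a break. The cost is a few sentences, one added documentation step, and a PI who does not see the result. While editing, correct the cross-reference in the same paragraph: it points to a section 4.10, and Section 4 ends at 4.3.

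A change to mixed or larger blocks is not recommended for this trial. It would remove the certainty (with blocks of 6, a revealed placebo leaves each block-mate a (2 - 1)/(6 - 1) = 1/5 chance of placebo). But this version is dated 07/01/2024 and the Synopsis ends the study on 09/20/2024, which is 30 + 31 + 20 = 81 days later, against 168 + 28 = 196 days of treatment and follow-up. On those dates few or no randomizations are likely to remain, and deleting the block size would not remove what investigators already know.
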